4 STUDY POPULATION

4.1 Enrollment

Subjects are eligible for enrolment into the study if they meet all of the inclusion criteria and eligibility criteria and do not meet any of the exclusion criteria.

4.1.1 Inclusion Criteria at Screening

Subjects must satisfy all of the following criteria to be included in the study:

1. Male and female subjects between the age of 18 to 75 years
2. Subjects with end stage renal disease (CKD stage 5*) on epoetin treatment for at least 3 months prior to screening
3. Subjects with haemoglobin between 10 g/dl to 12 g/dl
4. Subjects who are on clinically stable haemodialysis (defined as no clinically relevant changes of dialysis regimen and/or dialyzer) for at least 3 months prior to screening
5. Subject who had an adequacy of dialysis treatment measured by Kt/V
 - a. Kt/V must be ≥ 1.2 for subjects with 3 times of HD/week
 - b. Kt/V must be ≥ 1.8 for subjects with 2 times of HD/week
6. Subjects willing to provide a written informed consent
7. Subjects with serum ferritin $\geq 200 \mu\text{g/L}$ and/or transferrin saturation $\geq 20\%$
8. Subjects with a life expectancy more than at least study period in clinical judgment of the investigator

*CKD staging will be based on the five-stage system for classification of CKD based on KDIGO guidelines (page no: 32).

GFR will be calculated based on the EPI equation as below ([18](#))

$$\text{GFR} = 141 \times \min(S_{\text{cr}} / \kappa, 1)^{\alpha} \times \max(S_{\text{cr}} / \kappa, 1)^{-1.209} \times 0.993^{\text{Age}} \times 1.018 \text{ [if female]} \times 1.159 \text{ [if black]}$$

where:

S_{cr} is serum creatinine in mg/dL,
 κ is 0.7 for females and 0.9 for males,
 α is -0.329 for females and -0.411 for males,
min indicates the minimum of S_{cr} / κ or 1, and
max indicates the maximum of S_{cr} / κ or 1.

4.1.2 Eligibility criteria at Baseline

Subjects must satisfy all of the following criteria to be included in the study:

1. Subjects with stable haemoglobin levels between 10 g/dl to 12.5 g/dl with stable EPREX dosage and intra-individual change in Hb of $\leq 1.2 \text{ g/dl}$ over 4 weeks before randomization
2. Subjects with serum ferritin $\geq 200 \mu\text{g/L}$ and/or transferrin saturation $\geq 20\%$

Patients who don't meet the eligibility criteria at baseline will be considered as screen failures.

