The guidelines recommends to perform a ‘maintenance phase’ study using IV epoetin (e.g. in a haemodialysis population) for demonstration of similar efficacy of administration between the bio-similar product and the reference bio-similar product. The recommended choice of the reference product for erythropoietin bio-similar products, epoetin alfa is EPREX.

The maintenance phase study is designed to minimise baseline heterogeneity and carry over effects of previous treatments. Subjects included in a maintenance phase study will be optimally titrated on the reference product (EPREX) (stable haemoglobin in the target range on stable epoetin dose and regimen without transfusions) for duration of at least 3 months. In substantiated cases a prolongation of the titration period is allowed up to maximum of 4 to 5 months on a case to case basis which will be considered as extended titration period. The assessment will be similar to the visit 7 (week 12) if there is prolongation of the titration period. Thereafter, study subjects should be randomised to the EPIAO or continued on EPREX, maintaining their pre-randomisation epoetin dosage, dosing regimen and route of administration (IV).

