1.3 Risks and Benefits for Study Subjects

Recombinant erythropoietins (epoetin) have a relatively wide therapeutic window and are usually well tolerated provided that the stimulation of bone marrow is controlled by limiting the amount and rate of haemoglobin increase. The rate of haemoglobin increase may vary considerably between subjects and is dependent not only on the dose and dosing regimen of epoetin but also other factors, such as iron stores, baseline haemoglobin and endogenous erythropoietin levels, and the presence of concurrent medical conditions such as inflammation. In subjects with CKD, treatment of anaemia with r-HuEPO has improved cardiovascular function and the quality of life

to a greater extent. However, treatment with r-HuEPO to target haemoglobin concentrations of 13 g/dL or more (achieved mean concentrations >11 g/dL or 12 g/dL) has been consistently associated with high rates of cardiovascular disease, especially in subjects who are ESA-hypo responsive. Exaggerated pharmacodynamic response may result in hypertension and thrombotic complications. Moreover, PRCA due to neutralising anti-erythropoietin antibodies has been observed, predominantly in renal anaemia subjects treated with subcutaneously administered epoetin. Antibody-induced PRCA is a very rare event and usually takes months to years of epoetin treatment to develop. Clinical decision making should balance risks and benefits and usually favours r-HuEPO administration in subjects undergoing dialysis in whom haemoglobin concentrations are lower, quality of life is poorer, and transfusion is needed more often than for subjects with earlier stages of chronic kidney disease. ([17](#))

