
	Current Haemoglobin			
Changes in Hb over past 4 weeks	Hb < 10.5 g/dl)	Hb 10.5 to 12.0 g/dl	Hb 12.1 to 13.0 g/dl	Hb > 13.0 g/dl

Note:

- The iron status should be assessed and need to supplement, if required.
- The dose of the study medication will be rounded off to the highest value. E.g. if subject requires dose of 9000 IU, the dose will be rounded off to 10000 IU because of availability of study medication PFS in multiples of 2000 IU.
- The criteria mentioned about dose adjustment above are recommendation only, Investigator must act for the best interest of the patient whenever necessary

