5.1.9 Concomitant Medications

Concomitant therapy will be permitted based on the investigator's discretion. Detailed history of concomitant medications at the baseline will be recorded in the CRF. All concomitant therapy taken by the subject during the study period will be recorded in the CRF in the concomitant medication section in detail.

Subjects will be instructed to report to the investigator any medication used over the course of the study. The investigator will address the significance of the reported medication use on study integrity. At the discretion of the investigator, these subjects may continue study participation if the medication is not anticipated to alter study integrity.

The medications that permitted are

- Iron supplements
- Folic acid
- Alkalizing agents
- Phosphate binder (i.e. Calcium carbonate)

Subjects will receive oral iron supplements if TSAT is < 20% and will continue on iron supplements to maintain the TSAT $\geq 20\%$.

Allopurinol and Angiotensin Converting Enzyme (ACE) inhibitors if required are permitted at doses not affecting the efficacy of study drug at the discretion of the investigators.

Androgens are not recommended as an adjuvant to epoetin therapy ([3](#)).

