- The investigational product must be temporarily withheld until the result of immunogenicity assessments is shown negative, IP can be re-started upon confirmation of negative test for immunogenicity..

Fecal occult blood test

This test will be performed during screening visit as per PI discretion

Iron study

- Serum ferritin level
- Transferrin saturation (TSAT)
- Serum iron

- Total Iron Binding Capacity (TIBC) (optional)

These tests will be performed during screening, baseline visit (visit 8/Week 13/Day 91), visit 11 (week 16/Day 112), visit 13 (week 24/ Day 168), visit 16 (week 36/Day 252), visit 19 (week 48/Day 336) and visit 23 (week 64/ Day 448).

Intact parathyroid hormone level

This test will be performed during screening visit

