9.4 Efficacy Analyses

9.4.1 Primary Efficacy Analyses

- Mean absolute change in haemoglobin level from baseline to 6 months after treatment with EPIAO/EPREX in parallel groups (g/dl).
- Mean absolute change in weekly epoetin dosage per kg body weight from baseline to 6 months after treatment with EPIAO/EPREX in parallel groups (IU/kg/week).

The ANCOVA will be performed based on the normality of data for mean change between baseline to 6 months of EPIAO and EPREX with center, Hb level and weight as covariates. The 95% confidence intervals will be calculated for the treatment differences and is compared with pre-defined acceptance ranges: ± 0.5 g/dl for haemoglobin.

The ANCOVA will be performed based on the normality of data for mean change in weekly epoetin dosage per kg body weight baseline to 6-month treatment with EPIAO and EPREX with center, Hb level and weight as covariates. The 95% confidence intervals will be calculated for the treatment differences and is compared with pre-defined acceptance ranges: ± 45 IU/kg/week for dosage.

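### Both co-primary ANCOVAs leave out baseline iron status, which the protocol names as a driver of response and measures at Visit 8; adjusting for it is a small, nearly free gain in precision

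*Protocol*

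**What the plan says.** - **Entry.** Section 4.1.2, criterion 2, asks for serum ferritin of at least 200 μg/L "and/or transferrin saturation" of at least 20%. Section 4.1.1, criterion 7, uses the same either/or rule at screening.
- **Iron treatment.** Section 5.1.9 states: "Subjects will receive oral iron supplements if TSAT is < 20% and will continue on iron supplements to maintain the TSAT" at 20% or above. The rule does not mention ferritin, names no arm and is not limited to the period after randomisation. Iron supplements are also on that section's list of permitted medications. A note in 5.1.7 adds: "The iron status should be assessed and need to supplement, if required".
- **Measurement.** Sections 6.3 and 8.5 schedule an iron study (ferritin, TSAT, serum iron) at Visit 8, the randomisation visit. One is also done at screening. A footnote in 6.2 and the visit table place another at week 10, although the list in 8.5 does not repeat it.
- **Relevance.** Section 1.3 says the rate of haemoglobin increase depends on dose, regimen and "other factors, such as iron stores, baseline haemoglobin and endogenous erythropoietin levels". Section 1.2 says: "The maintenance phase study is designed to minimise baseline heterogeneity and carry over effects of previous treatments".
- **Analysis.** Section 9.4.1 specifies both co-primary ANCOVAs "with center, Hb level and weight as covariates". The 95% intervals are compared with ±0.5 g/dl and ±45 IU/kg/week.

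**The concern.** The protocol names two baseline drivers of response side by side and fixes a model that uses one of them. The other is measured at the same visit and left out. The either/or criterion ensures that iron status differs between subjects at randomisation. Some will have TSAT below 20% with ferritin of at least 200 μg/L, and others low ferritin with TSAT of at least 20%.

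Iron-related movement in haemoglobin, and in dose through the haemoglobin-driven adjustments of 5.1.7, then stays in the residual error of both equivalence intervals. A chance difference between arms in the share of such subjects is also left unadjusted. What is at stake is interval width against the two margins, and so the power to show equivalence.

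**Working it through.** **Inputs from the protocol.** 112 evaluable subjects per group and more than 80% power (9.8); margins 0.5 g/dl and 45 IU/kg/week; two-sided 95% interval (9.4.1).

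**Inputs that must be assumed.** p is the share of randomised subjects with TSAT below 20%; by the entry rule these all have ferritin of at least 200 μg/L. d is the mean shift that iron produces in them, equal in both arms. The SD of change is also not given.

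**The plan's own figure.** The 112 per group cannot be reproduced, because 9.8 gives no SD or assumed true difference. It can be solved backwards. With a true difference of 0, power = 2Φ(margin/(SD·√(2/n)) − 1.96) − 1. For 80% power on one endpoint, the largest SD is margin/(1.960 + 1.282) × √(112/2):
- Hb: 0.5/3.242 × 7.483 = 1.154 g/dl
- dose: 45/3.242 × 7.483 = 103.9 IU/kg/week

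**Step 1: main case, Hb, SD 1.0 g/dl.** The variance share explained is R² = p(1−p)d²/SD².
- p = 0.1, d = 0.5: 0.09 × 0.25 = 0.0225
- p = 0.3, d = 0.8: 0.21 × 0.64 = 0.134

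The interval narrows by 1 − √(1−R²), which is 1.1% to 7.0%. The half-width before adjustment is 1.96 × √(2/112) = 0.262 g/dl. After adjustment it is 0.259 to 0.244 g/dl.

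**Step 2: chance imbalance.** The SD of the between-arm difference in the share is √(2p(1−p)/112), which is 0.040 at p = 0.1 and 0.061 at p = 0.3. Multiplied by d, this is a shift with SD 0.02–0.03 g/dl for d = 0.5 and 0.03–0.05 g/dl for d = 0.8. For an assumed dose shift of 25 IU/kg/week it is 1.0–1.5 IU/kg/week.

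This is not a second loss on top of Step 1. The unadjusted interval already allows for it through its residual variance.

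**Step 3: wider range at the back-solved SDs (unadjusted power 80%).**

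| Endpoint | p | d | R² | Adjusted power | Equivalent n per group | 95% range of chance shift |
|---|---|---|---|---|---|---|
| Hb | 5% | 0.25 | 0.2% | 80.1% | 111.8 | ±0.014 |
| Hb | 10% | 0.5 | 1.7% | 81.0% | 110.1 | ±0.039 |
| Hb | 30% | 0.5 | 3.9% | 82.2% | 107.6 | ±0.060 |
| Hb | 30% | 1.0 | 15.8% | 88.4% | 94.3 | ±0.120 |
| Dose | 5% | 15 | 0.1% | 80.1% | 111.9 | ±0.86 |
| Dose | 20% | 30 | 1.3% | 80.8% | 110.5 | ±3.1 |
| Dose | 30% | 60 | 7.0% | 83.9% | 104.2 | ±7.2 |

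Equivalent n is 112(1−R²). With an SD of 0.8 g/dl for Hb, R² can reach 33% at the extreme corner (p = 30%, d = 1.0), but unadjusted power is then already 99.3%.

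**Step 4: direction of the errors.** Three things would make the gain smaller. R² is computed for a perfectly captured yes/no indicator, which TSAT and ferritin as covariates need not recover. Subjects already on iron before Visit 8 would shift less. Dose adjustment under 5.1.7 pulls haemoglobin back towards target.

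**The case against.** The case against is strong on several points.

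- **A randomised comparison does not need every prognostic covariate.** This stands. The model already has center and the two stratification variables, and omitting a further factor is inefficient rather than wrong. Section 1.3 also names other influences that are not in the model, such as inflammation and endogenous erythropoietin. The reply is narrow: iron status is named, measured at baseline and free to use. A SAP might add it, but the protocol states the covariate list outright.
- **A reader might infer that the entry criterion contradicts 5.1.9**, treating one iron state as adequate for entry and as needing treatment. The documents do not support this. They never call subjects who pass the criterion iron-adequate, and an entry rule and a supplementation trigger can differ.
- **A reader might infer that iron starts at the switch and drives the change from baseline.** Iron is tested at screening and at week 10, and the rule in 5.1.9 applies during titration, so many affected subjects would already be supplemented. Subjects must also have haemoglobin change of at most 1.2 g/dl over four weeks on a stable dose. The inference fits only those first found low at Visit 8. That is more likely after extended titration, whose assessments list no iron study.
- **A reader might infer that low-ferritin subjects with TSAT of at least 20% get no iron.** Iron is not mandated for them, but 5.1.9 permits it and the note in 5.1.7 calls for it if required.
- **A reader might infer bias between arms.** The iron rule names no arm and investigators are blinded. The primary population is per-protocol, so randomisation does not strictly guarantee balance in it, but nothing in the documents indicates that iron-related exclusions would differ by arm.

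**Conclusion.** The point holds as a minor matter of efficiency. Both co-primary models omit a baseline factor that the protocol itself names as a driver of response and already collects. The co-primary tests remain valid without it.

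The gain is small. With p of 10–30%, d of 0.5–0.8 g/dl and SD of 1.0 g/dl, the Hb interval narrows by about 1–7%. Over the wider range at the back-solved SDs, power rises from 80% to between 80.1% and 88.4% for Hb, and to between 80.1% and 83.9% for dose. The top of each range needs the most extreme assumed values. The documents supply neither p, d nor SD, and earlier supplementation would push the result towards the low end.

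The differing iron thresholds are not an error in the plan.

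**What to change.** In section 9.4.1 and the matching synopsis text, or in the SAP, add Visit 8 TSAT and ferritin as continuous covariates in both co-primary ANCOVAs, with ferritin suitably transformed (for example, log scale). Fix this before the unblinded interim analysis of section 9.6, so that the choice cannot depend on treatment results. State how a missing Visit 8 value is handled, for example by the last value before randomisation, so that the added covariates do not remove subjects from the model.

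The cost is two degrees of freedom and a line or two of text. No new data are needed.

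Optionally, the sponsor could reconcile the iron criteria in 4.1.1 and 4.1.2 with the trigger in 5.1.9, or explain in one sentence why they differ. Which threshold applies is a clinical decision for the sponsor, and none is proposed here.

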4.1.3 Exclusion Criteria at Screening

Subjects who meet any of the following criteria will be disqualified from entering the study:

1. Subjects with anaemia due to other reasons (that is not renal anaemia)
2. Subjects receiving blood transfusion within the last 3 months
3. Subjects requiring epoetin dose of $> 300 \text{ IU/kg/week}$
4. Subjects with major complication such as severe/chronic infections or bleeding, or aluminum toxicity
5. Subjects with suspected or known PRCA
6. Subjects with a history of aplastic anaemia
7. Subjects with uncontrolled diabetes (fasting blood glucose $> 240 \text{ mg/dl}$) or uncontrolled hypertension (systolic blood pressure $> 180 \text{ mm Hg}$, diastolic blood pressure $> 110 \text{ mm Hg}$)
8. Subjects with HbA1C $> 6.5\%$
9. Subjects with known hypersensitivity to any of the ingredients of the investigational products, the mammalian cell-derived product or human albumin products
10. Subjects with history of seizure disorder

11. Subjects with hematological disorder (thrombocytopenia: platelet count below $100 \times 10^9/L$, neutropenia: neutrophil count below $1.0 \times 10^9/L$, or hemolysis)
12. Subjects with hyperparathyroidism (intact parathyroid hormone $> 1000 \text{ pg/ml}$)
13. Subjects with alanine aminotransferase (ALT), aspartate aminotransferase (AST) and alkaline phosphatase levels $3 \times$ upper limit of normal (ULN) at screening
14. Subjects with **decompensated** congestive heart failure (NYHA class III and IV) **within 6 months prior to screening**
15. Subjects with angina (functional class III and IV) within 6 months prior to screening
16. Subjects with myocardial infarction or stroke in the preceding 6 months
17. Subjects with active malignancy in the previous 5 years
18. Subjects with gastrointestinal bleeding in the past 6 months
19. Subjects with immunosuppressive therapy in the previous 3 months
20. Subjects with active hepatitis B virus (positive for HBsAg and IgM anti-HBc **in Thailand and positive for HBsAg in Russia**)
21. Subjects with hepatitis C virus (HCV) (positive for Anti-HCV antibody)
22. Female subjects who are pregnant, breast-feeding, planning to be pregnant during the study, or women of child-bearing potential (any woman who is not surgically sterile i.e. bilateral tubal ligation, total hysterectomy or < 2 years post menopause) not using a reliable method of double contraception (e.g. condom plus diaphragm, condom or diaphragm plus spermicidal gel/foam, tubal ligation, or stable dose of hormonal contraception) throughout the study period
23. Subjects participating in trials involving long acting erythropoietin in the past 6 months before screening and short acting erythropoietin in the past 3 months before screening”
24. Subjects currently participating or participation in an investigational study within 30 days prior screening

4.2 Removal of Subjects from Therapy

4.2.1 Reasons for Withdrawal/Early Discontinuation

Any subject, who discontinues from the study treatment for any reason, will have his/her study treatment discontinuation recorded.

Subjects withdrawn prior to randomization but after signing informed consent:

- Screen Failure
- Withdrawal by Subject
- Investigator Decision

Subjects withdrawn after randomization but before completing the study as per protocol:

- Adverse Event as per PI discretion

- If subjects develop anti-epoetin antibodies or PRCA or severe allergic reaction
- If the subject requires epoetin dose more than 300 IU/kg/week
- Death
- Lost to Follow-up
- Pregnancy
- Progressive Disease
- Study Terminated by Sponsor
- Withdrawal by Subject

If a subject withdraws from the study, the investigator will complete and report the observations as thoroughly as possible up to the date of withdrawal including the date of last treatment and the reason for withdrawal.

If the subject is withdrawn due to an adverse event, the investigator will follow the subject until the adverse event has resolved or stabilized.

All subjects who are withdrawn from the study, effort should be made to complete protocol specified withdrawal procedures (Section 4.2.2).

4.2.2 Withdrawal Procedures

Subjects who discontinue will be asked about the reason(s) for their discontinuation and about the presence of any adverse events. If a subject withdraws or is discontinued from the study before completion, every effort should be made to complete the last scheduled assessments. The PI must provide a written report on the appropriate CRF page describing the reason for discontinuation. The primary reason for the withdrawal must also be recorded in subject's medical record along with CRF. Adverse events should be followed up and all investigational products should be returned by the subject. All study procedures, including collection of efficacy and safety variables, should be conducted and recorded on the appropriate CRF. The final report will include reasons for withdrawal.

4.2.3 Subject Replacement

The subjects who do not complete the study will be considered dropouts and will not be replaced.

4.2.4 Subject Re-screening Procedures

Patients who are diagnosed with end stage renal disease (Stage 5) receiving hemodialysis and epoetin treatment but excluded for other reasons are allowed to be re-screened once in this study based on the clinical judgment of the investigator.

5 TREATMENTS ADMINISTERED

5.1 Investigational Product(s)

The Investigator must ensure that the investigational product (IP) will be used only in accordance with the protocol. The drug will be manufactured complying with all required regulations. Sufficient quantities of the drug will be supplied to the clinical study facility by the sponsor. Batch

numbers and expiration dates will be filed in the study documents when available. See the table below for ingredient list of each product.

Table 1: Investigational Product Details

	Treatment	Comparator
Active Ingredient	Recombinant human erythropoietin	Recombinant human erythropoietin
Brand name	EPIAO	EPREX
Dosage form	Pre-filled syringe	Pre-filled syringe
Strength	2000 IU, 4000 IU	2000 IU, 4000 IU
Frequency	1-3 times per week	1-3 times per week
Route of administration	Intravenous	Intravenous
Manufactured by	Shenyang Sunshine Pharmaceutical Co., Limited	Janssen Pharmaceuticals, Inc.

For the purpose of this trial, study medication / study drug / study treatment / investigational product / IP refer to EPIAO of Shenyang Sunshine Pharmaceutical Co., Limited and EPREX of Janssen Pharmaceuticals, Inc.

